### **12.3 Safety Laboratory**

Blood samples will be collected at the time points specified in the schedule of events (refer to the Protocol) to conduct haematology, serum chemistry, and coagulation analyses.

#### **12.3.1 Endpoints**

Hematology:

- Hemoglobin
- Leukocytes
- Neutrophils
- Eosinophils
- Monocytes
- Lymphocytes
- Basophils
- Platelets
- Other

Serum Chemistry:

- Sodium
- Potassium
- Calcium
- Magnesium
- Phosphate
- Creatinine
- Albumin
- AST
- ALT
- Alkaline phosphatase
- Total bilirubin
- eGFR
- Other

Coagulation:

- aPTT
- INR

All laboratory data collected at scheduled and unscheduled visits will be included in the listings, but only results collected as scheduled visits will be included in the summary tables excepts for baseline assessment where unscheduled visit prior to first study medication could be considered for baseline summary.

Results for individual parameters may be reported in different units depending on the analysing laboratory. If required, the results (and the corresponding normal range cut-off values) for

individual parameters may be converted to International System of Units (S.I.) units to summarize the data.

For all the parameters where a unit value has been reported, the parameter names that will be used in the outputs will comprise of the test name and the unit of measure, for example, 'Albumin (g/L)'. For the urinalysis parameters, the parameter name will be the reported test name only. Parameters will be sorted alphabetically within tables and listings.

For all parameters where a normal range limit value was reported, the normal range will be derived based on the available lower and upper limit values and any reported mathematical symbols. If both a lower and upper limit value is available, the normal range will be presented as '(Lower, Upper)'.

The reported results for each parameter with a defined normal range will be classified ('Low', 'Normal', 'High') in relation to the defined normal range limits. If a result is equal to the normal range cut-off value, the result will be considered 'Normal'.

The decimal precision to which the summaries for each parameter will be based on the maximum number of decimals to which the reported result or the normal range limits are presented to in the raw data. The results and normal ranges will be displayed to the same decimal precision in the listings.

If a result for a parameter that is normally considered continuous is reported as a range (i.e., the result for basophils is reported as '<0.01' for a single time point), the result may be converted to a numeric as noted in section 3.5 to contribute to the derivations and the summary statistics. Any conversion rules that are applied will be highlighted in the footnotes of the affected tables and listings. The original reported result value will however be included in the listing.

The haematology, coagulation and serum chemistry results tables will present summary statistics for each laboratory parameter within the specific test panel. For each parameter, summaries will be presented for the baseline and each scheduled post-baseline visit. In addition, summaries will be presented for the change from baseline values at each scheduled post-baseline visit.

Additionally, counts (%) of number participants with values out of normal range at each scheduled time point will also be presented along with shift tables that will represent the changes in normal range categories across post-baseline time points. Clinical significance for out of range values will be listed only.

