4.3 Safety Criteria for Stopping Dosing

Advancing to the next dose cohort will be done after review of safety data by the PI and the Sponsor's Medical Monitor, both of whom are unblinded as to treatment assignment in Part A and blinded as to treatment assignment in Part B. If a dose is safe, then the next dose cohort will be enrolled. Criteria that would result in a pause in active dosing and further investigation by the study team include if any subject experiences a SAE deemed related to the study drug; if two or more subjects experience the same grade 3 or higher AE; if accumulation of SAEs and/or AEs collectively raises a safety concern in the opinion of the investigator, research monitor, or study sponsor; or if any subject experiences an adverse event of special interest (AESI).

If a subject develops a significant allergic reaction or anaphylaxis following study drug administration, the study drug will be immediately discontinued for that subject and no further doses given. The PI should contact the Sponsor's Medical Monitor to determine whether to discontinue study treatment for a given subject. Regardless of communication with the Sponsor, the PI is authorized to discontinue the study drug at any time if it is in the best interest of the safety of the subject. Treatment may also be discontinued at the request of the subject.

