5.1 Inclusion Criteria

A subject must fulfill all the following criteria to be eligible for enrollment:

- 1. Male or female between 18 and 50 years, inclusive, at time of informed consent
- 2. Willingness to participate after written informed consent obtained
- 3. Available for all planned clinical visits for physical examinations, blood draws, stool collections
- 4. General good health, without significant medical illness or abnormal physical examination findings as determined by the PI.
- 5. Adequate safety laboratory results, renal and liver function.
 - a. Absolute neutrophil count $\ge 1.5 \times 10^9/L$
 - b. Lymphocyte count < $6.0 \times 10^9/L$
 - c. Platelet count $\ge 150 \times 10^9/L$
 - d. Hemoglobin ≥ 110 g/L
 - e. $eGFR \ge 40 \text{ mL/min/1.73 m}^2$
 - f. ALT and/or AST \leq 3x ULN
 - g. Total bilirubin ≤ 1.5x ULN
 - h. Serum albumin \geq 28 g/L
- 6. Females of childbearing potential should be using and committed to continue using one of the following acceptable birth control methods:
 - a. Sexual abstinence (inactivity) or exclusively same-sex partner for 1 month prior to screening through study completion; or
 - b. IUD in place for at least 1 month prior to study through study completion; or
 - c. Stable hormonal contraception for at least 1 month prior to study through study completion; or
 - d. Surgical sterilization (vasectomy) of male partner at least 6 months prior to study.
- 7. To be considered of non-childbearing potential, females should be surgically sterilized (bilateral tubal ligation, hysterectomy, or bilateral oophorectomy at least 2 months prior to study) or be post-menopausal and at least 12 months since last menses.
- 8. Male participants must use condoms during the study and through study completion.

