8.3 Recording Adverse Events

AEs spontaneously reported by the subject and/or in response to an open question from the study personnel or revealed by observation will be recorded during the study at the investigational site. Clinically significant changes in laboratory values, blood pressure, and pulse need not be reported as AEs since they will be captured in those data listings. However, abnormal values that constitute an SAE or lead to discontinuation of administration of treatment must be reported and recorded as an AE. Information about AEs will be collected from the signing of the consent form until the end of the study. SAE information will be collected from signing of the consent form until 28 days following the last dose of treatment. The AE term should be reported in standard medical terminology when possible. For each AE, the Investigator will evaluate and report the onset (date and time), resolution (date and time), intensity, causality, action taken, serious outcome (if applicable), and whether or not it caused the subject to discontinue the study.

Intensity will be assessed according to the CTCAE Version 5.0. A pdf of these criteria is attached as Appendix A.

It is important to distinguish between serious and severe AEs. Severity is a measure of intensity whereas seriousness is defined by the criteria under the Section above entitled Serious Adverse Event. An AE of severe intensity may not be considered serious.

Should a pregnancy occur, it must be reported and recorded in the source documents and Medical History form in the CRF. Pregnancy is not regarded as an AE unless there is a suspicion that an investigational product may have interfered with the effectiveness of a contraceptive medication.

The outcome of all pregnancies (spontaneous miscarriage, elective termination, normal birth or congenital abnormality) must be followed up and documented even if the subject was discontinued from the study.

All reports of congenital abnormalities/birth defects are SAEs. Spontaneous miscarriages should also be reported and handled as SAEs. Elective abortions without complications should not be handled as AEs.

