## 17. TABLES

No.	Title	Analysis Set
	PARTICIPANT DISPOSITION AND ANALYSIS SETS	
14.1.1	Summary of Participant Enrollment and Disposition	Safety
	DEMOGRAPHIC AND BASELINE INFORMATION	
14.1.2	Summary of Demographics and Baseline Characteristics	Safety
14.1.3	Summary of Medical History, by SOC and PT	Safety
14.1.4	Summary of Study Drug Compliance for Part B	Safety
	PHARMACOKINETIC ANALYSIS	
14.2.1.1	Summary of Serum Concentrations of VHH by Timepoint	PK
14.2.1.2	Summary of Serum PK Parameters of VHH	PK
	SAFETY	
14.3.1.1	Summary of Concomitant Medication	Safety
14.3.3.1	Overall Summary of Treatment-Emergent Adverse Events	Safety
14.3.3.2	Summary of Treatment-Emergent Adverse Events, by SOC and PT	Safety
14.3.3.3	Summary of Serious Treatment-Emergent Adverse Events, by SOC and PT	Safety
14.3.3.4	Summary of Treatment-Emergent Adverse Events by Toxicity, by SOC and PT	Safety
14.3.3.5	Summary of Treatment-Emergent Adverse Events by Relationship, by SOC and PT	Safety
14.3.4.1.1	Summary of Hematology & Coagulation by Timepoint	Safety
14.3.4.1.2	Summary of Hematology & Coagulation Shifts from Baseline (Low, Normal, High)	Safety
14.3.4.1.3	Summary of Hematology & Coagulation Shifts from Follow-up (Low, Normal, High)	Safety
14.3.4.2.1	Summary of Serum Chemistry by Timepoint	Safety
14.3.4.2.2	Summary of Serum Chemistry Shifts from Baseline (Low, Normal, High)	Safety

14.3.4.2.3	Summary of Serum Chemistry Shifts from Follow-up (Low, Normal, High)	Safety
14.3.4.4.1	Summary of Vital Signs by Timepoint	Safety
14.3.4.4.2	Summary of Vital Signs Shifts from Baseline (Low, Normal, High)	Safety
	IMMUNOGENICITY	
14.4.1	Summary of Immunology by Timepoint	Safety
14.4.2	Summary of Immunology Shifts from Baseline (Low, Normal, High)	Safety

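### The laboratory shift tables sort results only as Low, Normal or High, so no table counts participants by how severe a laboratory change was

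*SAP*

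**What the plan says.** SAP 12.3.1 sets the classification: "The reported results for each parameter with a defined normal range will be classified ('Low', 'Normal', 'High') in relation to the defined normal range limits". A value on the limit is not out of range: "If a result is equal to the normal range cut-off value, the result will be considered 'Normal". The categorical laboratory summaries are counts of participants out of range at each scheduled time point and "shift tables that will represent the changes in normal range categories across post-baseline time points". SAP 17 carries this into the table list: Table 14.3.4.2.2 is "Summary of Serum Chemistry Shifts from Baseline (Low, Normal, High"), and Table 14.3.4.1.2 does the same for hematology and coagulation. The follow-up versions (14.3.4.1.3 and 14.3.4.2.3) use the same three categories. Clinical significance of out-of-range values goes to listings only.

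SAP 12.3.1 also plans summaries of the values and of change from baseline at each scheduled visit. Shells 14.3.4.1.1 and 14.3.4.2.1 show n, mean, SD, median, minimum and maximum.

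Protocol 5.1, inclusion 5, sets two entry limits as multiples of the upper limit of normal: ALT and/or AST up to 3x, and "Total bilirubin ≤ 1.5x ULN". Protocol 3.3 counts clinically significant abnormal laboratory tests as part of the safety assessment. For adverse events, Protocol 8.3 states: "Intensity will be assessed according to the CTCAE Version 5.0". The same section exempts clinically significant laboratory changes from adverse event reporting, because the data listings hold them, unless they constitute an SAE or lead to discontinuation of treatment.

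**The concern.** A shift table is where a reader looks first for participants whose laboratory results got worse. With three categories it answers one question: did the result cross a reference limit? It says nothing about how far. Two situations follow.

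- A participant who enters above the limit, as the eligibility criteria allow for ALT, AST and bilirubin, cannot show further worsening on that test. The person stays in the High-to-High cell.
- A participant who enters within range and leaves it falls in the same cell whether the excess is trivial or large. This needs no abnormal baseline, so it can affect anyone.

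The graded adverse event summary (Table 14.3.3.4) does not fill the gap reliably, because Protocol 8.3 does not require most laboratory changes to be reported as adverse events. At stake is whether the report can state, by dose group, how many participants had a laboratory change of a given severity.

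**Working it through.** There is no planned power, alpha or effect size on this point, so there is no figure of the plan's own to reproduce. Planned enrolment adds up: 2 + 3 x (4 + 2) = 20.

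**Step 1: apply the SAP rule at the protocol's entry limits.** Inputs: the rule in SAP 12.3.1 (above the upper limit is High, equal to it is Normal) and the limits in Protocol 5.1. Values are in multiples of ULN; the post-baseline values are illustrative.

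| Test | Baseline | Post-baseline | Change | Cell |
|---|---|---|---|---|
| ALT/AST | 3.0 | 3.09 | +0.09 | High to High |
| ALT/AST | 3.0 | 6 | +3 | High to High |
| ALT/AST | 3.0 | 15 | +12 | High to High |
| ALT/AST | 3.0 | 1.01 | -1.99 | High to High |
| Bilirubin | 1.5 | 3 | +1.5 | High to High |
| Bilirubin | 1.5 | 7.5 | +6 | High to High |
| Either | 1.0 | 1.01 | +0.01 | Normal to High |
| Either | 1.0 | 15 | +14 | Normal to High |

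From a High baseline, a negligible rise, a fivefold rise and a clear improvement look alike. From a normal baseline, a 1% excess and a 15-fold value look alike.

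**Step 2: see what the companion table shows.** Take one dose group of 4 (Protocol 4.1), with three participants unchanged and one rising from 3x to 15x ULN. The changes are 0, 0, 0 and 12.

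- Mean = 12/4 = 3.0.
- Median = 0.
- SD = sqrt[(3 x 3² + 9²)/3] = sqrt(108/3) = 6.0.
- Maximum = 12.

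The event shows in the mean, SD and maximum, but not in the median or the shift table. The summary does not tie the maximum to that participant's baseline, and it does not count participants by severity.

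**Step 3: how often could a High baseline occur?** The documents give no frequency. Assume a proportion p of participants enter out of range on a given test. The chance of at least one among n is 1 - (1 - p)^n.

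| Assumed p | One dose group, n = 4 | All participants, n = 20 |
|---|---|---|
| 2% | 8% | 33% |
| 5% | 19% | 64% |
| 10% | 34% | 88% |
| 20% | 59% | 99% |

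This range bears only on the High-to-High problem. The Normal-to-High problem does not depend on it.

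**Step 4: check for a severity count elsewhere.** In the SAP 17 and 18 lists, Table 14.3.3.4 grades adverse events, not laboratory values. Listings 16.2.8.1.2 and 16.2.8.2.2 show abnormal values one by one. No table grades laboratory results or bands them by multiples of ULN.

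**The case against.** The best reply is that the information is in the report. The change-from-baseline tables carry the minimum and maximum at every scheduled visit, and the abnormal-result listings give each value with its change, reference range, flag and clinical significance. With 4 active participants per dose, the maximum is one person whom a reader can look up. Protocol 3.3 itself asks for comparison with laboratory normal ranges and assigns CTCAE to adverse events, so the SAP format follows the protocol. Inclusion 4 requires general good health, which may make High baselines uncommon. All of this stands, and it limits the point to a missing severity count.

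Four stronger readings are tempting, and the documents do not support them.

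- A reader might infer that mild and severe laboratory changes cannot be told apart anywhere in the analysis. That is true of the shift tables only.
- A reader might infer that hemoglobin, albumin and eGFR have a matching Low-to-Low problem, given entry limits of 110 g/L, 28 g/L and 40 mL/min/1.73 m². That depends on reference limits the documents do not give. Out-of-range entry is allowed by construction only for ALT, AST and bilirubin.
- A reader might infer that the pause rule is weakened, since one of its criteria is graded: "if two or more subjects experience the same grade 3 or higher AE". That criterion concerns adverse events reviewed while cohorts are being dosed. The shift tables belong to the final analysis after database lock (SAP 15.2) and do not feed it.
- A reader might infer that chance out-of-range results will swamp the tables. A count of chance flags needs assumed reference coverage and independence between related tests, and it measures neither masked worsening nor shifts.

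**Conclusion.** The point holds for the shift tables. Large worsening from a High baseline on ALT, AST or bilirubin is tabulated as no shift, and from a normal baseline all degrees of excess share one cell. The classification result follows directly from the SAP rule and the protocol's entry limits. How often a High baseline will occur rests on an assumption, shown above as a range.

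The consequence is modest. No estimate, test or sample size changes, and individual values remain available. What the report would lack is a count of participants by laboratory severity. That matters because Protocol 3.3 makes clinically significant abnormal laboratory tests part of the safety assessment, while Protocol 8.3 leaves most of them outside the graded adverse event tables. The addition is worth making because it costs little.

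**What to change.** Keep Tables 14.3.4.1.2 and 14.3.4.2.2 as they are, since they deliver the normal-range comparison in Protocol 3.3. Add one table, by treatment group, of baseline CTCAE v5.0 grade against worst post-baseline grade for each parameter that has a laboratory grade in that version. For analytes that can be abnormal in either direction, show high and low separately; a single 0 to 4 grade in place of the current categories would lose direction. For ALT, AST and bilirubin, bands in multiples of ULN would also serve.

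The SAP text should list the graded parameters, taken from the criteria the protocol attaches as Appendix A. It should also say whether the worst value includes unscheduled results, which SAP 3.1 currently keeps out of summary tables.

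The cost is a small amount of programming from results and reference limits already collected, with no new visits or samples. The chemistry shift shell has to be rewritten anyway, because it shows a 25 mg group, study days and a programming note that do not belong to this trial. Parameters without a grade keep the current format.

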## **12.4 Vital Signs**

The following vital signs measurements will be taken at the time points specified in the Schedule of Events (refer to the Protocol).

### **12.4.1 Definition of variables**

- Heart Rate (beats/min),
- Systolic blood pressure (SBP) (mmHg),
- Diastolic blood pressure (DBP) (mmHg),
- Respiratory rate (breaths/min),
- Temperature (°C).

All vital signs data collected at scheduled and unscheduled visits will be included in the listings, but only results collected as scheduled visits will be included in the summary tables.

The parameter names that will be used in the outputs will comprise of the test name and the unit of measure, for example, 'Systolic Blood Pressure (mmHg)'. Parameters will be sorted in

the order that the measurements were collected in on the Vital Signs eCRF page within the tables and listings.

The change from baseline to the pre-dose assessment at each post-baseline visit will be calculated for all parameters. An assessment of clinical significance for each result will be reported.

The decimal precision to which the summaries for each parameter will presented will be based on the maximum number of decimals to which the results were reported on the eCRF.

Vital signs measurements will present summary statistics for the results at the baseline and each scheduled post-baseline visit for each of the parameters. In addition, summaries will be presented for the change from baseline values and interpretation of each result at each scheduled post-baseline visit.

The listings of vital signs measurements will include all the information collected. In addition, the observations that are used as the baseline record (value) for each parameter will be flagged, and the change from baseline values at each post-baseline visit will be presented.

### **12.5 Physical Examination**

Full physical examination and targeted physical assessments will be listed for all time points.

### **12.6 Pregnancy Test Results**

All information related to pregnancy testing (urine and serum based) will be listed. This listing will include all pregnancy test results collected during the study.

### **13. IMMUNOGENICITY**

Immunogenicity endpoints will be analysed using the PK analysis set if systemic absorption of LMN-101 is observed. Listings will be presented as specified in section 3.1 by treatment group.

#### **13.1 Serum anti-VHH IgG antibodies**

Serum samples will be collected at baseline, Day 28 (Part B only), and end of study for measuring for antidrug antibodies if systemic absorption of LMN-101 is observed. If anti-drug antibodies are observed, additional determinations will be performed for antibodies. If antibodies are observed on confirmatory assays, additional testing will be done to measure antibody titers.

Immunogenicity assessments will be listed for all time points.

#### **14. CHANGES TO THE PLANNED ANALYSIS**

No changes to the biostatistical methods planned in the protocol were made.

## **15. INTERIM AND FINAL ANALYSIS**

### **15.1 Interim Analyses**

An interim dataset of serum VHH concentration data will be produced by an unblinded biostatistician in the form of an Excel® spreadsheet and provided to Lumen Biosciences. The dataset, blinded to subject and treatment data, will determine if PK analysis and Anti-VHH antibody testing is required.

### **15.2 Final Analysis (End of Study)**

The final analysis will be conducted after all participants have completed the study, the clinical database has been locked, the analysis sets have been approved and the study has been unblinded.

The final analysis will be based on the final version of the SAP. Any deviations from the planned analysis will be documented in the CSR.

## **16. SOFTWARE**

The following software will be used to perform the statistical analyses:

- SAS® Version 9.2 or higher (SAS Institute, Cary, North Carolina, USA.)
- Phoenix WinNonlin version 8.1 or higher (Certara USA, Inc., Princeton, NJ, USA.)

## 17. TABLES

No.	Title	Analysis Set
	PARTICIPANT DISPOSITION AND ANALYSIS SETS	
14.1.1	Summary of Participant Enrollment and Disposition	Safety
	DEMOGRAPHIC AND BASELINE INFORMATION	
14.1.2	Summary of Demographics and Baseline Characteristics	Safety
14.1.3	Summary of Medical History, by SOC and PT	Safety
14.1.4	Summary of Study Drug Compliance for Part B	Safety
	PHARMACOKINETIC ANALYSIS	
14.2.1.1	Summary of Serum Concentrations of VHH by Timepoint	PK
14.2.1.2	Summary of Serum PK Parameters of VHH	PK
	SAFETY	
14.3.1.1	Summary of Concomitant Medication	Safety
14.3.3.1	Overall Summary of Treatment-Emergent Adverse Events	Safety
14.3.3.2	Summary of Treatment-Emergent Adverse Events, by SOC and PT	Safety
14.3.3.3	Summary of Serious Treatment-Emergent Adverse Events, by SOC and PT	Safety
14.3.3.4	Summary of Treatment-Emergent Adverse Events by Toxicity, by SOC and PT	Safety
14.3.3.5	Summary of Treatment-Emergent Adverse Events by Relationship, by SOC and PT	Safety
14.3.4.1.1	Summary of Hematology & Coagulation by Timepoint	Safety
14.3.4.1.2	Summary of Hematology & Coagulation Shifts from Baseline (Low, Normal, High)	Safety
14.3.4.1.3	Summary of Hematology & Coagulation Shifts from Follow-up (Low, Normal, High)	Safety
14.3.4.2.1	Summary of Serum Chemistry by Timepoint	Safety
14.3.4.2.2	Summary of Serum Chemistry Shifts from Baseline (Low, Normal, High)	Safety

14.3.4.2.3	Summary of Serum Chemistry Shifts from Follow-up (Low, Normal, High)	Safety
14.3.4.4.1	Summary of Vital Signs by Timepoint	Safety
14.3.4.4.2	Summary of Vital Signs Shifts from Baseline (Low, Normal, High)	Safety
	IMMUNOGENICITY	
14.4.1	Summary of Immunology by Timepoint	Safety
14.4.2	Summary of Immunology Shifts from Baseline (Low, Normal, High)	Safety

